## **16. APPENDICES**

### **16.1 Study information**

#### **16.1.1 *Protocol and protocol amendments***

The following documents are enclosed:

- Clinical study protocol, Final version 1.0, 28JUL14
- Protocol amendment No. 1, Final version 2.0, 25NOV14

## STUDY SYNOPSIS

Title: Two-way crossover, randomised, single-dose and two-stage bioequivalence phase I study of ketoprofen lysine salt as immediate release tablets formulation (40 mg) versus ketoprofen lysine salt as granules for oral solution (80 mg bipartite sachet, half sachet) after oral administration to healthy volunteers of both sexes
Protocol number: CRO-PK-14-288 - Sponsor study code KSL0114
Clinical phase: Phase I
Study design: Single centre, single-dose, open, randomised, two-way cross-over, two-stage bioequivalence study
Planned nr. of centres / countries: 1/Switzerland
Sponsor: Dompé s.p.a. [name] Milan offices: [name] - Italy
Investigator and centre: Principal Investigator: [name]; Co-Investigator: [name], FMH; Cross Research Phase I Unit, [name], Switzerland
Investigational product(s): TEST (T): Ketoprofen lysine salt (KLS), immediate release tablets 40 mg, corresponding to 25 mg as ketoprofen, Dompé s.p.a., Italy REFERENCE (R): OKI®, 80 mg granules for oral solution (bipartite sachets), each half sachet containing 40 mg of KLS corresponding to 25 mg as ketoprofen, Dompé s.p.a., Italy
Dose regimen: A single oral dose (40 mg) of each formulation (test and reference) will be administered to healthy volunteers under fasting conditions in two consecutive study periods with a wash-out interval of at least 4 days between the two administrations.
Objective: To investigate the bioequivalence between two formulations containing ketoprofen lysine salt (KLS) when administered as single oral dose in two consecutive study periods to healthy male and female volunteers under fasting conditions.
End-points: Primary end-point: to evaluate the bioequivalent rate ( $C_{max}$ ) and extent ( $AUC_{0-t}$ ) of absorption of ketoprofen after single dose administration of test and reference. Secondary end-points: 
 
➤ to describe the pharmacokinetic (PK) profile of ketoprofen after single dose administration of test and reference;
 
➤ to collect safety and tolerability data after single dose administration of test and reference.
 

Study variables: Primary variables: $C_{max}$ and $AUC_{0-t}$ of ketoprofen calculated from plasma concentrations after single oral dose of test and reference. Secondary variables: 
 
➤ <math>AUC_{0-\infty}</math>, <math>t_{max}</math>, <math>t_{1/2}</math>, <math>\lambda_z</math> and <math>F_{rel}</math> of ketoprofen calculated from plasma concentrations after single oral dose of test and reference;
 
➤ Treatment-emergent AEs (TEAEs), vital signs (BP, PR, BT), body weight, ECG, laboratory parameters
 

Analytics: Ketoprofen free acid will be determined in plasma by a HPLC-UV validated assay at Dompé Bioanalytical Laboratories, L'Aquila, Italy. Analytical facilities and procedures are in compliance with GLP regulations.
Safety and tolerability assessments: Treatment-emergent adverse events (TEAEs); vital signs (blood pressure [BP], pulse rate [PR], body temperature [BT]), body weight, physical examinations; laboratory tests performed at screening and final visit/early termination visit (ETV); electrocardiogram (ECG) at screening and final visit/ETV

## STUDY SYNOPSIS (cont.)

**Sample size:** in a first study stage 30 healthy volunteers (at least 12 subjects per sex) will be included and treated receiving test and reference treatment according to the cross-over design. Drop-out subjects will not be replaced. After the end of study stage 1, PK parameters will be calculated and an *ad interim* bioequivalence test will be performed on the calculated PK parameters  $C_{\max}$ ,  $AUC_{0-t}$  and  $AUC_{0-\infty}$ . To safeguard the overall type I error, the Pocock spending function will be used to determine the  $\alpha$  level of the bioequivalence test. Should bioequivalence be proven with the results of the subjects of the first stage and with an *a posteriori* calculated power of at least 80%, the primary objective of the study would then be satisfied and the second study stage will not take place. Should bioequivalence not be proven with the results of the subjects of the first stage or should it be proven with an *a posteriori* calculated power lower than 80%, the overall sample size for the study (stage 1 plus 2) will be calculated on the basis of the *ad interim* bioequivalence results. The Sponsor will decide whether the study has to continue or not. In the first case, the additional subjects will be enrolled into the second study stage. After completion of stage 2, the PK analysis and the bioequivalence test will be performed on the pooled subjects of the two study stages. The second stage will be performed after notification of the sample size to the local Ethics Committee and to the central Swiss authority (Swissmedic).

### Main selection criteria:

#### Inclusion criteria:

1. *Informed consent:* signed written informed consent before inclusion in the study
2. *Sex and Age:* males/females, 18-55 years old inclusive
3. *Body Mass Index (BMI):* 18.5-30 kg/m^2 inclusive
4. *Vital signs:* systolic blood pressure (SBP) 100-139 mmHg, diastolic blood pressure (DBP) 50-89 mmHg, pulse rate (PR) 50-90 bpm and body temperature (BT)  $\leq$  37.5° C, measured after 5 min of rest in the sitting position;
5. *Full comprehension:* ability to comprehend the full nature and purpose of the study, including possible risks and side effects; ability to co-operate with the investigator and to comply with the requirements of the entire study
6. *Contraception and fertility (females only):* females of child-bearing potential and with an active sexual life must be using at least one of the following reliable methods of contraception:
  - a. Hormonal oral, implantable, transdermal, or injectable contraceptives for at least 2 months before the screening visit
  - b. A non-hormonal intrauterine device [IUD] or female condom with spermicide or contraceptive sponge with spermicide or diaphragm with spermicide or cervical cap with spermicide for at least 2 months before the screening visit
  - c. A male sexual partner who agrees to use a male condom with spermicide
  - d. A sterile sexual partner

Female participants of non-child-bearing potential or in post-menopausal status for at least 1 year will be admitted. For all female subjects, pregnancy test result must be negative at screening.

#### Exclusion criteria:

1. *Electrocardiogram (ECG 12-leads, supine position):* clinically significant abnormalities
2. *Physical findings:* clinically significant abnormal physical findings which could interfere with the objectives of the study
3. *Laboratory analyses:* clinically significant abnormal laboratory values indicative of physical illness
4. *Allergy:* ascertained or presumptive hypersensitivity to the active principles (ketoprofen) and/or formulations' ingredients; history of hypersensitivity to drugs (in particular to NSAIDs) or allergic reactions in general, which the Investigator considers may affect the outcome of the study
5. *Diseases:* significant history of renal, hepatic, gastrointestinal, cardiovascular, respiratory (including asthma), skin, haematological, endocrine or neurological and autoimmune diseases that may interfere with the aim of the study
6. *Medications:* medications, including over the counter (OTC) drugs [in particular ketoprofen and acetylsalicylic acid (ASA), and NSAIDs in general], herbal remedies and food supplements taken 2 weeks before the start of the study. Hormonal contraceptives for females will be allowed
7. *Investigative drug studies:* participation in the evaluation of any investigational product for 3 months before this study. The 3-month interval is calculated as the time between the first calendar day of the month that follows the last visit of the previous study and the first day of the present study (date of the informed consent signature)

## STUDY SYNOPSIS (cont.)

### Exclusion criteria (cont.):

8. *Blood donation*: blood donations for 3 months before this study
9. *Drug, alcohol, caffeine, tobacco*: history of drug, alcohol [ $> 1$  drink/day for females and  $> 2$  drinks/day for males, defined according to the USDA Dietary Guidelines 2010 (6)], caffeine ( $> 5$  cups coffee/tea/day) or tobacco abuse ( $\geq 6$  cigarettes/day)
10. *Drug test*: positive result at the drug test at screening
11. *Alcohol test*: positive alcohol breath test at day -1
12. *Diet*: abnormal diets ( $< 1600$  or  $> 3500$  kcal/day) or substantial changes in eating habits in the 4 weeks before this study; vegetarians
13. *Pregnancy (females only)*: positive or missing pregnancy test at screening or day -1, pregnant or lactating women

### Schedule:

Visit	Day	Procedures/Assessments	Notes
Screening – visit 1	From day -14 to day -2	
 
➤ Explanation to the subject of study aims, procedures and possible risks
 
➤ Informed consent signature
 
➤ Screening number (as S001, S002, etc.)
 
➤ Demographic data and life style recording
 
➤ Medical/surgical history
 
➤ Previous/concomitant medications
 
➤ Full physical examination (body weight, height, vital signs, physical abnormalities)
 
➤ ECG recording
 
➤ Laboratory analyses: haematology, blood chemistry, urine analysis, serum virology and serum pregnancy test (females only)
 
➤ Urine multi-drug kit test
 
➤ AE monitoring
 
➤ Inclusion/exclusion criteria evaluation
 
➤ Eligibility evaluation
 
	
Note: The first two letters of the surname followed by the first two letters of the first name will be used in the clinical centre source document only and will not be transferred to the sponsor

Visit 2	Day -1	
 
➤ Alcohol breath test
 
➤ Vital signs measurement
 
➤ Urine pregnancy test (females only)
 
➤ AE and concomitant medications
 
➤ Inclusion/exclusion criteria evaluation
 
➤ Eligibility evaluation
 
➤ Enrolment and Randomisation
 
	
Arrival at the clinical centre in the evening    Confinement until the evening of day 1    Standardised low-fat dinner    Fasting for at least 10 h (overnight)

Visit 3	Day 1	
 
➤ IMP administration: <math>8:00 \pm 1h</math>
 
➤ Vital signs measurement: 8h post-dose
 
➤ Blood sample collection for PK analysis: pre-dose (0), 5, 15, 30, 45 min, 1, 1.5, 2, 3, 4, 5, 6 and 8 h post-dose
 
➤ AE and concomitant medications
 
	
Day 1    Standardised lunch at 13:00 (5 h post-dose)    Discharge from the clinical centre in the evening after the 8 h blood sample collection and vital signs check

## STUDY SYNOPSIS (cont.)

Schedule (cont.):			
Wash-out	At least 4 days	A wash-out interval of at least 4 days between the two administrations of the two study periods	
Visit 4	Day -1	As visit 2, with the exclusion of Inclusion/exclusion criteria evaluation, Eligibility evaluation, Enrolment and Randomisation	Arrival at the clinical centre in the evening Confinement until the evening of day 1 Standardised low-fat dinner Fasting for at least 10 h (overnight)
Visit 5	Day 1	As visit 3. Test or reference IMP administered according to the randomisation list and cross-over design	Day 1 Standardised lunch at 13:00 (5 h post-dose) Final discharge from the clinical centre after the 8 h blood sample collection and final visit
Final Visit/ETV	Day 1 of period 2 / at ETV in case of discontinuation	
 
➤ Full physical examination (body weight, physical abnormalities and, in case of ETV, vital signs)
 
➤ ECG recording
 
➤ Laboratory analyses as at screening, with the exception of serum virology, urine drug test and pregnancy test
 
➤ AE and concomitant medications
 
 
In case of clinically significant results at the final visit, the subjects will be followed-up by the investigator until the normalisation of the concerned clinical parameter(s)
	Upon leaving, the subjects will be instructed to contact immediately the investigator in case of occurrence of any adverse reactions

During confinement, the subjects will not take any food or drinks (except water) for at least 10 h (i.e. overnight) before IMP administration. Water will be allowed as desired, except for one h before and two h after IMP administration. In order to maintain an adequate hydration, the subjects will be encouraged to drink at least 180 mL of mineral water every 2 h for 6 h post-dose, starting at 2 h post-dose. In the evening of day -1, the subjects will receive a standardised light and low-fat dinner. On day 1 of each study period, the subjects will remain fasted until 5 h post-dose. Standardised lunch will be served at approximately 5 h post-dose. Coffee, tea and any other food containing xanthines (i.e. coke, chocolate, etc.) will be forbidden during confinement. Alcohol and grapefruit will be forbidden from 48 h before the first administration until the end of the study. During confinement, routine ambulant daily activities will be strongly recommended. The subjects will be allowed to smoke not more than 1 cigarette after lunch.
			

**STUDY SYNOPSIS (cont.)****Data analysis:**

The PK analysis and the statistical analysis of PK parameters will be performed using Phoenix WinNonlin® version 6.3 or higher, Pharsight Corporation and SAS® version 9.3 (TS1M1) or higher. The statistical analysis of safety data will be performed using SAS® version 9.3 (TS1M1) for Windows or higher.  $C_{max}$  and AUC will be compared between T and R using analysis of variance (ANOVA) for a cross-over design on log-transformed data. ANOVA will be performed on the data from stage 1 and, if applicable, the combined data from stage 1 and stage 2. The statistical analysis will take into account treatment, period, sequence and subject (sequence) as source of variation in the first stage. If the analysis of combined data from the two stages is required, stage, treatment, period (stage), sequence, sequence\*stage and subject (sequence\*stage), will be taken into account as source of variation. Acceptance criterion for bioequivalence is a 94.12% confidence interval for the T/R ratio of the geometric means of the parameters under consideration within the 80.00-125.00% range, according to the current guidelines for bioequivalence studies and to the Pocock  $\alpha$  spending function.  $t_{max}$  will be analysed using the non-parametric Friedman test. The data documented in this trial and the measured clinical parameters will be described using classic descriptive statistics for quantitative variables and frequencies for qualitative variables

**Timing:**

EC meeting: 26AUG14; planned clinical phase: NOV14; planned reporting: 25 working days after availability of analytical results

## STUDY SCHEDULE

ACTIVITIES	Screening	PERIOD 1, 2 (wash-out at least 4 days)		
		V1	V2, V4	V3, V5
Visit	Days -14/-2	Day -1	Day 1	Final/Early Termination Visit (ETV) 
Informed consent	x			
Demography	x			
Lifestyle	x			
Medical history and underlying disease	x			
Physical abnormalities	x			x
Previous and concomitant treatments	x	x	x	x
Height	x			
Body weight	x			x
Alcohol breath test		x		
Laboratory analysis	x			x
Virology	x			
Drug screening	x			
BP, PR, BT	x	x	x 	x 
Pregnancy test	x	x		
ECG	x			x
Inclusion/exclusion criteria evaluation	x	x 		
Eligibility evaluation	x	x 		
Enrolment and Randomisation		x 		
Confinement		x		
Discharge			x	
Drug administration			x	
Blood samplings			x	
Standardised meals		x	x	
AEs monitoring	x	x	x	x

1. Full laboratory analysis will be performed at screening visit. The same analysis will be performed at final visit with the exclusion of virology, drug screening and serum pregnancy test
2. at 8 h post-dose, corresponding to the final visit assessment at the end of period 2; at early termination visit (if applicable)
3. Females only. Serum β-HCG test at screening visit; urine test at the clinical centre on day -1 of each study period
4. at  $8:00 \pm 1$  h
5. Pre-dose (0), 5, 15, 30, 45 min, 1, 1.5, 2, 3, 4, 5, 6 and 8 h post-dose
6. Standardised meal will be served at approximately 5 h after the 1st drug administration. A standardised light and low-fat dinner will be served on day -1 of each period
7. AEs will be monitored from the screening visit, immediately after informed consent, up to the final visit.
8. on day 1 of period 2, after the 8 h blood sampling and vital signs check, subjects will undergo a final visit. In case of discontinuation, subjects will undergo an ETV
9. On visit 2 only

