## **10.6 Safety and tolerability evaluation**

### ➤ **AEs**

Adverse events (AEs) will be coded by System Organ Class (SOC) and Preferred Term (PT), using the Medical Dictionary for Regulatory Activities (MedDRA). AEs will be classified as pre-treatment AEs (PTAEs) and treatment-emergent AEs (TEAEs), according to the period of occurrence, as follows:

- PTAEs: all AEs occurring before the first dose of IMP and not worsening after the first dose of IMP
- TEAEs: all AEs occurring or worsening after the first dose of IMP

Individual PTAEs and TEAEs will be listed in subject data listings. No summary table will be provided for PTAEs. TEAEs will be summarised by treatment and overall. The number and percentage of subjects with any TEAE and the number of TEAEs will be tabulated by SOC and PT, seriousness, relationship to treatment and severity.

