- 3: Females only. Serum β-HCG test at screening visit; urine test at the clinical centre on day -1 of each study period
- 4: at 8:00 ± 1 h
- 5: Pre-dose (0), 5, 15, 30, 45 min, 1, 1.5, 2, 3, 4, 5, 6 and 8 h post-dose
- 6: Standardised lunch was served at approximately 5 h post-dose. A standardised light and low-fat dinner were served on day -1 of each period
- 7: AEs were monitored from the screening visit, immediately after informed consent, up to the final visit.
- 8: on day 1 of period 2, after the 8 h blood sampling and vital signs check, subjects underwent a final visit. In case of discontinuation, subjects underwent an ETV
- 9: At visit 2 only

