6.1 Analysis sets

6.1.1 Definitions

A subject will be defined as screened after the signature of the informed consent, regardless of the completion of all the screening procedures.

A subject will be defined as eligible if he/she meets all the inclusion/exclusion criteria. Otherwise he/she will be defined as a screen failure.

A subject will be defined as enrolled in the study if he/she is included into the interventional phase of the study. The enrolment was performed through randomised allocation to a treatments sequence.

An eligible but not enrolled subject will be defined as a reserve.

A subject will be defined as randomised in the study when he/she is assigned to a randomised treatments sequence.

- Enrolled set: all enrolled subjects. This analysis set will be used for demographic, baseline and background characteristics
- Safety set: all subjects who receive at least one dose of the investigational medicinal product(s). This analysis set will be used for the safety analyses
- PK set: all randomised subjects who fulfil the study protocol requirements in terms of investigational medicinal product(s) intake and have evaluable PK data readouts for the planned treatment comparisons, with no major deviations that may affect the PK results. This analysis set will be used for the statistical analysis of the PK results

Each subject will be coded by the CRO Biometry Unit as valid or not valid for the Safety set and the PK set. Subjects will be evaluated according to the treatment they actually receive.

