6.6 Safety evaluation

6.6.1 Adverse events

Adverse events (AEs) will be coded by System Organ Class (SOC) and Preferred Term (PT), using the Medical Dictionary for Regulatory Activities (MedDRA) version 17.1.

AEs will be classified as pre-treatment AEs (PTAEs) and treatment-emergent AEs (TEAEs), according to the period of occurrence, as follows:

- PTAEs: all AEs occurring before the first dose of IMP and not worsening after the first dose of IMP
- TEAEs: all AEs occurring or worsening after the first dose of IMP

Individual PTAEs and TEAEs will be listed in subject data listings.

No summary table will be provided for PTAEs.

TEAEs will be summarised in tables of frequency. The number and percentage of subjects with any TEAE, the number of TEAEs, the number and percentage of subjects with any TEAE by severity, the number of TEAEs by severity, the number and percentage of subjects with any TEAE related to study drug and the number of TEAEs related to study drug will be presented.

Serious TEAEs will be summarized by treatment. Should any serious TEAE occur, the number and percentage of subjects with any serious TEAE, the number of serious TEAEs, the number and percentage of subjects with any serious TEAE related to study drug and the number of serious TEAEs related to study drug will be presented.

All TEAEs leading to death, Serious TEAEs and TEAEs leading to discontinuation will be listed, if occurring.

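### Scheduled adverse event collection lasts at least 4 days after a period 1 dose but about 8 h after a period 2 dose, so by-treatment percentages can understate later-onset TEAEs by up to one half; SAP 6.6.1 also specifies by-treatment tables only for serious TEAEs

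*Protocol*

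**What the plan says.** **Collection window.** Footnote 7 of the protocol's Study Schedule states: "AEs will be monitored from the screening visit, immediately after informed consent, up to the final visit". Footnote 8 fixes when that is: "on day 1 of period 2, after the 8 h blood sampling and vital signs check, subjects will undergo a final visit". Footnote 7 to Table 1 in SAP 2.3 keeps the same end point: "AEs were monitored from the screening visit, immediately after informed consent, up to the final visit". The doses are separated as follows: "A wash-out interval of at least 4 days between the two administrations of the two study periods". AEs are asked about again at visit 4, the evening before the second dose.

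**After the final visit.** Subjects are told to contact the investigator if an adverse reaction occurs (protocol 6.1). A 24-hour mobile line takes SAE calls (11.7). AEs are followed to outcome or to 10 days after the final visit (11.9). A telephone follow-up appears only as a possibility in the definition of last subject last visit (6.1). No contact to ask about new AEs is scheduled.

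**Definition and tables.** Protocol 10.6 defines "TEAEs: all AEs occurring or worsening after the first dose of IMP", with no window per dose, and adds: "TEAEs will be summarised by treatment and overall", as numbers and percentages of subjects. SAP 6.6.1 has: "TEAEs will be summarised in tables of frequency". It says by treatment only for serious TEAEs. SAP 1.1, which lists changes from the protocol, does not mention this.

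**Laboratory tests and ECG.** Both are done at screening and at the final or early termination visit only. Clinically significant abnormalities after screening must be recorded as AEs (protocol 10.6; SAP 6.6.3 and 6.6.6).

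**The concern.** Collecting safety and tolerability data after a single dose of test and of reference is a secondary end-point. In a crossover, each product's AE table mixes doses given in period 1 with doses given in period 2. Here the two have very different observation times, yet they would share one denominator. An event that starts the evening after dosing, or the next day, would be picked up at visit 4 if it followed dose 1. If it followed dose 2, it would be missed unless the subject called. The percentage for later events would then look lower than the data support, and the absence of such events would look more informative than it is. If, in addition, non-serious TEAEs are not separated by product, the tables do not deliver what protocol 10.6 promised.

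**Working it through.** **Inputs.** The documents give no AE rate, onset-time data or safety precision target, so there is no safety figure to reproduce. The one design figure used is 15 subjects per sequence, 30 in all (SAP 6.2.1). It comes from the bioequivalence calculation, which does reproduce: with T/R 1.053, CV 20% and one-sided alpha 0.0294, exact power of the two one-sided tests is 89.1% at 28 subjects and 91.2% at 30, so 30 is the smallest even number reaching 90%. SAP 6.5 reports the stage 1 analysis on 30 randomised subjects.

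**Step 1, windows.** After dose 1: at least 4 × 24 = 96 h. After dose 2: about 8 h. Ratio: at least 96/8 = 12. Each product has 15 period 1 doses and 15 period 2 doses. Scheduled coverage per product is 15 × 96 + 15 × 8 = 1,560 subject-hours, or 54% of the 30 × 96 = 2,880 that equal 96 h windows would give.

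**Step 2, later-onset events.** Let p be the risk per dose of a TEAE starting between 8 h and 96 h. Assume that recall at visit 4 is complete, that an event is assigned to the last product taken, and that a fraction c of late events after dose 2 is reported by unsolicited call. Then:

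reported percentage = (15p + 15cp)/30 = p(1 + c)/2

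This runs from p/2 (c = 0, nothing reported) to p (c = 1, everything reported). With c = 0 and illustrative values of p:

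| Assumed p | Subjects expected with equal windows (30p) | Subjects expected under the plan (15p) | Percentage shown on 30 |
|---|---|---|---|
| 5% | 1.5 | 0.75 | 2.5% |
| 10% | 3 | 1.5 | 5% |
| 20% | 6 | 3 | 10% |

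**Step 3, seeing none.** At p = 10%, the chance of no late event on a product is 0.9^15 = 20.6% with 15 observable doses and 0.9^30 = 4.2% with 30. As a yardstick, the one-sided 95% upper bound after zero events is 1 − 0.05^(1/15) = 18.1% on 15 doses and 1 − 0.05^(1/30) = 9.5% on 30.

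**Step 4, all TEAEs together.** Early events are fully captured, so the overall loss is smaller. Take independent early and late risks, with c = 0.
- Early 10%, late 5%: with equal windows 1 − 0.90 × 0.95 = 14.5%. Under the plan ½ × 14.5% + ½ × 10% = 12.3%, a ratio of 0.84.
- Early 10%, late 10%: 19.0% becomes 14.5%, a ratio of 0.76.

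**Step 5, test against reference.** Both products have the same 15/15 mix, so the factor (1 + c)/2 applies to each and the ratio of their late-event percentages is unchanged. Dropout after period 1 could disturb this, but the SAP reports 30 subjects in the analysis.

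**Step 6, attribution of final-visit findings.** In a subject who completes both periods, the only post-screening laboratory tests and ECG come after both products. Neither document says to which product an AE first detected there belongs.

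**The case against.** **Period 1 is not really observed for 4 days.** Subjects leave after the 8 h sample in both periods, and the rest of period 1 depends on memory at visit 4. This stands. The asymmetry is one scheduled question that covers the interval after dose 1 and has no counterpart after dose 2.

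**One half is a worst case, and late drug effects may be few.** Calls can recover events. With the stated half-life of 1–2 h, 8 h covers 4 to 8 half-lives, so later events may be mostly background. This also stands. The documents give no onset data, so the values of p above are illustrations only.

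**No inference is planned on these rates.** Safety is descriptive, and neither document plans a confidence bound or defines a 96 h window. The two bounds in Step 3 show how much information is present; they are not figures the trial would report.

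**The SAP does not say that TEAEs will be pooled.** SAP 1.1 lists no departure from protocol 10.6, so by-treatment tables may still be intended. A reader might infer that the secondary end-point goes unanswered. The documents support only that SAP 6.6.1 is silent where the protocol is explicit, while naming treatment for serious events.

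**Stronger readings to avoid.** A reader might infer that the unequal windows bias test against reference; the 15/15 allocation rules that out by design. A reader might also infer that laboratory or ECG findings at the final visit would be charged to the second product. No such rule is written; what is missing is any rule.

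**Conclusion.** The point holds, and it is minor. Scheduled AE collection differs by a factor of at least 12 between the two doses. A by-treatment percentage on about 30 subjects can therefore understate TEAEs starting more than 8 h after dosing, by up to one half if no event after the final visit is reported and by less if some are. This assumes complete recall at visit 4, all 30 subjects dosed in both periods, and assignment of each event to the last product taken. It does not touch events within 8 h, it tilts the comparison towards neither product, and it has no bearing on the bioequivalence result. The mismatch between SAP 6.6.1 and protocol 10.6 needs no assumption about onset times and should be corrected in any case.

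**What to change.** Amend SAP 6.6.1 before the safety analysis:

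1. Restore the TEAE tables of protocol 10.6, by treatment and overall.
2. Tabulate by treatment the TEAEs with onset within 8 h of dosing, with all doses of that product as denominator. Tabulate later-onset TEAEs separately, with period 1 doses only (about 15 per product) as denominator. List any event reported spontaneously after the final visit, and state that scheduled collection after the second dose ended at about 8 h.
3. Show AEs first detected by final-visit laboratory tests or ECG under overall only, because the schedule cannot attribute them to one product.

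The cost is a few lines of text, one extra table split and a smaller denominator for late events. All of it uses data already collected. A scheduled telephone question after the second dose would have evened out the windows, but it cannot help this trial: SAP 6.5 reports the stage 1 analysis as complete and says that stage 2 will not take place.
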